A total of 22 months is needed for 4 sites to randomize the total sample size of 128 in this second stage. The whole study duration for the second stage is expected to

be 46 months including 6 months of start-up, 22 months of enrollment, 6 months of follow-up, and 12 months of database search, study closure, and final data analysis. Upon approval, it is expected that the Dallas and Oklahoma City sites will begin recruitment almost immediately, followed by Nashville and Denver sites.

Estimated Enrollment for CCTA #0002 Phase II							
Site	PCI Volume as Reported by VA Cardiovascular Assessment, Reporting, and Tracking System for Cath Labs (CART-CL)		Annual ACS Indication, FY2014*	LDL > 70 mg/dL AND eGFR > 45 ml/min, FY2014*	Annual Eligible Patients	Monthly Eligible Patients	Monthly Accrual Target
	FY2013	FY2014					
Dallas	350	419	158	94	94	7.8	1.5
Oklahoma City	402	482	258	138	138	11.5	1.5
Nashville	250	313	173	110	110	9.2	1.5
Denver	132	210	115	58	58	4.8	1.5

*Eligibility criteria.

4(g)(iv). Statistical Analysis of Primary Effectiveness Endpoint:

The primary effectiveness outcome will be analyzed with intent-to-treat (ITT) approach by including all randomized patients regardless of crossover or drop-out. The change in total atheroma volume within a ≥ 20 mm long segment of the target coronary artery from baseline to 90 days will be analyzed using the two-sample t-test. We will define their change scores to be 0 if they do not have a 90-day atheroma volume measurement. Analysis of Covariance (ANCOVA) will be performed to evaluate the treatment effect on primary effectiveness outcome adjusting for age, pre-existing CAD, pre-existing diabetes, and baseline LDL levels.

4(g)(v). Statistical Analysis of Secondary Effectiveness Endpoints:

The intent-to-treat principle will also be applied to all the secondary effectiveness outcomes analyses.

- (1). The change of %NC component of atheroma from baseline to 90 days will be analyzed using the two-sample t-test. Similarly, the change scores for those who miss the 90 days follow up assessment will be set to zero. Analysis of Covariance (ANCOVA) will be performed to evaluate the treatment effect on primary effectiveness outcome adjusting for age, pre-existing CAD, pre-existing diabetes, and baseline LDL levels.

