4(g)(vii). Interim Monitoring: Hines CSPCC will produce a progress report every six months for review by Data Monitoring Committee. The report will include figures for patient accrual, tables for baseline characteristics, site performance, data quality, treatment compliance, and safety issues. Group sequential methods will be used to specify the α -levels in order to maintain the overall significance level at $\alpha = 0.05$ for the primary effectiveness hypothesis test. The sequential analyses will use O'Brien-Fleming boundaries with an overall $\alpha = 0.05$ for significance and 90% for power. EAST software was used to obtain the interim monitoring rule and the adjusted sample size. The look will be around 50% of the target sample size (about 64 patients) completing the 90-day follow-up visit as DMC recommended at its first meeting on September 25, 2009. The sample size remains at 128 to account for this extra interim look by assuming the groups mean difference of -1.26 and the pooled standard deviation of 1.922.

The interim look will cost 0.003 for α . If the critical value is greater than 2.9626 or less than -2.9626, the study will be stopped to reject the null hypothesis. However, if the critical value is between -2.9626 and 2.9626, the study will continue until the target sample size is met for final analysis.

4(g)(viii). Subgroup Analyses: Since acute coronary syndrome (ACS) is manifested as either unstable angina or non-ST-elevation myocardial infarction, both

safety and effectiveness outcomes will be analyzed for LDL-apheresis treatment effects in unstable angina subgroup and non-ST-elevation MI subgroup as well as the total ACS patients. In addition, separate analyses will be performed across 4 participating sites for each treatment group in order to evaluate the site effect and confirm the appropriateness of pooling the data for primary endpoint.

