4(g)(ix). Sensitivity Analysis for Missing Data: In addition to the above mentioned ITT principle for primary and secondary effectiveness outcomes in which the change scores will be set to zero if the follow-up assessment is missing, other approaches will be applied in order to assess the robustness of the study results to assumptions about the missing data. For outcomes about atheroma volume and % of NC component of atheroma which will be measured only at 2 time points, the sensitivity analysis approaches include: 1) performing analysis only on complete data, 2) applying the worst case scenario (set the lowest score at baseline and the highest score at 90-day), and 3) generating imputes for missing data with multiple imputation. For outcome about EPC-CFU/ml of peripheral blood which will be repeatedly measured at four time points, the sensitivity analysis approaches include: 1) performing analysis only on complete data, and 2) using the mixed model for repeated measures.

All tests will be two-sided. The critical level for all the primary and secondary outcomes will be 0.05. No adjustments will be made for multiple secondary endpoints.

4(h) Quality Assurance, Oversight and Study Regulation

4(h)(i) Training to assure accuracy, precision and validity of the data: Toward the end of the six-month start-up period, training of study personnel will take place during a two-day kick-off meeting. All participating investigators, site research coordinators/raters, and Hines CSPCC personnel will be in attendance. Prior to the meeting, case report forms will be finalized and a detailed manual of study operations will be written and circulated. This manual will serve as the training manual for the meeting and as a reference document following the meeting. The PI's office and the data and pharmacy coordinating centers will provide the training. The general training will include the study treatment, patient screening and consent, baseline evaluation, follow-up procedures, and proper entry and maintenance of data. Cyber security awareness training and privacy training (VHA Privacy Policy, Protection of Human Research Subjects, and Good Clinical Practices) are required annually of all VA and VA-WOC employees.

4(h)(ii). Data Management and Security

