## **Analysis of Primary Effectiveness Outcome**

The primary effectiveness outcome will be analyzed with intent-to-treat (ITT) approach by including all randomized patients regardless of crossover or drop-out. The change in total atheroma volume within a  $\geq 20$  mm long segment of the target coronary artery from baseline to 90-day follow-up will be analyzed using the two-sample t-test. We will define their change scores to be 0 if they do not have an atheroma volume measurement at 90-day follow-up. Analysis of Covariance (ANCOVA) will be performed to evaluate the treatment effect on primary effectiveness outcome adjusting for age, pre-existing CAD, pre-existing diabetes, and baseline LDL levels.

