## **Analysis of Secondary Effectiveness Outcomes**

The intent-to-treat principle will also be applied to all the secondary effectiveness outcomes analyses.

The change of %NC component of atheroma from baseline to 90-day follow-up will be analyzed using the two-sample t-test. The change scores for those who miss the 90-day follow-up assessment will be set to zero. Analysis of Covariance (ANCOVA) will be performed to evaluate the treatment effect on primary effectiveness outcome adjusting for age, pre-existing CAD, pre-existing diabetes, and baseline LDL levels.

The EPC-CFU/ml of peripheral blood assessed at 4 time points (pre-PCI, post-PCI, 30-day follow-up, and 90-day follow-up) will be analyzed via Mixed Linear models with random intercepts. The treatment effect, time effect and their interaction will be considered with or without adjusting for age, pre-existing CAD, pre-existing diabetes, baseline LDL levels, and other relevant covariates such as ACS, peripheral vascular disease, and chronic kidney disease. The statistical test of interest is the time by treatment interaction. Contrasts will be used in the Mixed Linear models to compare the differences among any specifically interested time points.

The incidence of major adverse cardiovascular endpoints (MACE) including death, myocardial infarction, coronary revascularization, and stroke will be analyzed in two ways. The percentage of people who experience the event at least once will be compared using the chi-square test. Logistic regression models will be performed to adjust for the covariates such as age, pre-existing CAD and pre-existing diabetes. An event-based analysis will also be done since MACE can be recurrent. In this analysis, a non-parametric method called the mean cumulative function (MCF) will be used as an alternative to the above crude incidence rate analyses. The overall safety profiles as well as the safety profiles in specific subgroups over the whole study period will be compared for the two randomization groups including the times of event recurrence and censoring mechanisms. Time to event (survival analysis) will also compare the time to first MACE between treatment groups. A second survival analysis will be performed to identify risk predictors and to evaluate whether the observed treatment effect is modified by adjusting for covariates such as pre-existing CAD and pre-existing diabetes.

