## **Handling Missing Data**

The Intent-to-treat (ITT) principle will be applied for primary and secondary effectiveness outcomes in which the change scores will be set to zero if the follow-up assessment is missing.

Other approaches will also be applied in order to assess the robustness of the study results for assumptions about the missing data. For outcomes about atheroma volume and % of NC component of atheroma which will be measured only at 2 time points, the sensitivity analysis approaches include: 1) performing analysis only on complete data, 2) applying the worst case scenario (set the lowest score at baseline and the highest score at 90-day follow-up), and 3) generating imputes for missing data with multiple imputation. For outcome about EPC-CFU/ml of peripheral blood which will be repeatedly measured at 4 time points, the sensitivity analysis approaches include: 1) performing analysis only on complete data, and 2) using the mixed model for repeated measures.

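### The primary analysis scores every missing 90-day atheroma volume as zero change, which shrinks the estimated effect by the drop-out fraction; the multiple imputation already planned should be primary

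*Protocol*

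**What the plan says.** Protocol 4(g)(iv) analyses all randomised patients with a two-sample t-test on change in total atheroma volume. For patients without the follow-up measurement it states: "We will define their change scores to be 0 if they do not have a 90-day atheroma volume measurement". The SAP, Analysis of Primary Effectiveness Outcome, has the same rule: "We will define their change scores to be 0 if they do not have an atheroma volume measurement at 90-day follow-up". The SAP section Handling Missing Data presents it as the intent-to-treat approach, "in which the change scores will be set to zero if the follow-up assessment is missing".

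The rule is also primary for %NC: Protocol 4(g)(v) has "the change scores for those who miss the 90 days follow up assessment will be set to zero" and the SAP, Analysis of Secondary Effectiveness Outcomes, has "The change scores for those who miss the 90-day follow-up assessment will be set to zero".

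Protocol 4(g)(ix) and the SAP section Handling Missing Data list three sensitivity analyses for these two outcomes: complete data only, a worst case, and "generating imputes for missing data with multiple imputation". Neither document gives the imputation model. The worst case reads "applying the worst case scenario (set the lowest score at baseline and the highest score at 90-day", which does not say whether the baseline is replaced only when it is itself missing.

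**The concern.** Keeping every randomised patient does not require giving the missing ones a change of zero; imputation keeps them too. Zero would be a sensible value if it were what the plan expected for an unmeasured patient. The sample-size section expects regression in one arm and progression in the other, and nothing in the documents says why a missed catheterisation should mean no plaque change. Each zero therefore pulls its arm's mean towards the other arm's.

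At stake is the headline result, both the size of the treatment difference and its confidence interval. A second risk arises if drop-out differs between arms while plaque changes in both. The rule then creates a difference where none exists, and it need not be conservative. Patients and site investigators know the treatment (Protocol 4(c)(v)(2)) and the endpoint needs a repeat catheterisation, so equal drop-out is not assured. The documents give no evidence of an imbalance, however.

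**Working it through.** **Inputs.** Protocol 4(g)(ii) gives mean changes of -0.38 (SD 2.08) in ILLT and +0.88 (SD 1.75) in SMT, 1:1 allocation, two-sided 0.05, 90% power, 20% drop-out and N = 128. Protocol 4(g)(vii) gives a difference of -1.26 and pooled SD of 1.922. These are areas in mm², while the endpoint is a volume, so only proportions carry over. The documents give one overall drop-out rate; equal rates by arm are assumed unless stated.

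**1. The plan's own figure.** A two-sample t-test at d = 0.65 needs 51 evaluable patients per arm for 90% power (exact power 90.2%). Then 51 / 0.8 = 63.75, so 64 per arm and N = 128, as stated. This inflation corresponds to about 51 completers per arm and the full difference, not to 64 per arm with a fifth scored as zero.

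**2. What the zero rule estimates.** With a fraction *p* missing at random in both arms, the expected difference is (1 - *p*)(-0.38) - (1 - *p*)(0.88) = (1 - *p*)(-1.26). At *p* = 0.20 this is -0.304 - 0.704 = -1.008.

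**3. Why power holds.** Each arm's variance becomes (1 - *p*)s² + *p*(1 - *p*)m².
- ILLT: 0.8 × 4.3264 + 0.16 × 0.1444 = 3.484
- SMT: 0.8 × 3.0625 + 0.16 × 0.7744 = 2.574
- Pooled SD: √((3.484 + 2.574)/2) = 1.740, down from 1.922

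The standardised effect is 1.008 / 1.740 = 0.579, and t-test power at 64 per arm is 90.2%.

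**4. Zero rule by drop-out rate** (40,000 simulated trials per row, normal changes):

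| Missing in each arm | Expected difference | 95% CI covers -1.26 | Power |
|---|---|---|---|
| 20% | -1.008 | 86.7% | 90.6% |
| 15% | -1.071 | 90.7% | 92.4% |
| 10% | -1.134 | 93.1% | 93.6% |
| 5% | -1.197 | 94.6% | 94.7% |

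**5. Multiple imputation at 20% missing** (by arm, 20 imputations, Rubin's rules with small-sample degrees of freedom, 12,000 trials):
- Baseline-only model: mean -1.257, SE 0.386, coverage 95.2%, power 89.6%.
- Model with baseline, site and all four ANCOVA covariates, none assumed to predict change: SE 0.404, coverage 96.0%, power 87.7%.
- For comparison, completers: SE 0.379, power 90.8%.

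The zero rule's SE of 0.307 belongs to a shrunken target. On the full-effect scale it is 0.307 / 0.8 = 0.384, so its narrower interval is not extra precision.

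**6. Interim look.** Take 32 per arm, an assumed 20% missing among them, the stated boundary of 2.9626, and a final boundary of 1.9686 (calculated for overall 0.05 at half information; the documents do not state it). Early stopping is 23.0% with zeros and 20.0% with baseline-only imputation; overall power is 90.2% and 89.2%. If the look counts only patients with a 90-day measurement, the two rules agree there.

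**7. Unequal drop-out, illustration only.** Assume no treatment effect, SD 1.922 and a common drift μ in both arms. The zero rule then produces a false difference of (p_SMT - p_ILLT)μ; for μ = +0.88 with 30% missing in ILLT and 10% in SMT, this is -0.176. Both the drifts and the splits are assumptions.

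| Drift | Missing ILLT/SMT | Two-sided type I error |
|---|---|---|
| +0.88 | 20/20 | 4.8% |
| +0.88 | 22/18 | 5.1% |
| +0.88 | 25/15 | 6.0% |
| +0.88 | 30/10 | 8.8% |
| +0.44 | 25/15 | 5.2% |
| +0.44 | 30/10 | 6.0% |
| 0 | 30/10 | 5.0% |

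Baseline-only imputation at +0.88 and 30/10 gives 4.5%.

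**The case against.** The strongest reply is that the decision is not harmed. The hypothesis is superiority, power is about 90%, and under equal drop-out the test is valid and the error in the estimate runs against the device. That is correct and limits the weight of the point. It does not rescue the estimate or its interval.

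Second, the unshrunken estimate will be produced anyway as a sensitivity analysis, and 20% is the upper end: the benchmark in Protocol 4(h)(iv) is below 20%, and Protocol 4(e) lets a clinically indicated catheterisation stand in for the study one. Both points reduce the size of the problem. At 5% missing it is small; at 10% the estimate is still 10% too small.

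Third, the protocol's interim trigger is "The look will be around 50% of the target sample size (about 64 patients) completing the 90-day follow-up visit", so few values should be missing at that look. This largely stands. The SAP's Plan for Interim Analysis, however, counts patients completing the 6-month visit, and such a patient could lack a 90-day volume.

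Fourth, the type I error illustrations need both a large drift and a large imbalance. The +0.88 is a one-year area change in familial hypercholesterolaemia patients; at 30/10 a drift of +0.20 gives only 5.3%. This stands, and the conclusion does not rest on them.

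Fifth, complete-case analysis does as well as baseline-only imputation on precision and power. That is true under these assumptions. Imputation is preferred because it keeps all randomised patients, as the plan intends. A short imputation model is not matched to the planned ANCOVA and makes missing at random a stronger assumption; the full model costs more power. That trade-off is real and should be settled in advance.

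**Conclusion.** The concern holds. With equal drop-out unrelated to outcome, the primary estimate is too small by exactly the drop-out fraction: at the planned 20% it targets 80% of the effect, and its nominal 95% interval covers the planned effect about 87% of the time. The proportion does not depend on units, so it applies to volume, and under the same drop-out assumption to %NC. The coverage figures rest on the planning means and SDs and on normal changes. Power is not lost, and the null test is sound when drop-out is equal. Bias in the test under unequal drop-out is possible but undocumented. This is a worthwhile and inexpensive improvement, not a flaw that invalidates the trial.

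**What to change.** In Protocol 4(g)(iv), 4(g)(v) and 4(g)(ix) and the matching SAP sections:

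- Make multiple imputation the primary handling of missing 90-day volume and %NC. Impute separately by arm, keeping all randomised patients and the planned t-test.
- Prespecify the model and the number of imputations. Use the baseline value plus only those covariates expected to predict change, and say how this relates to the ANCOVA.
- State how patients who die before the 90-day measurement enter the analysis; an imputed volume needs justification there.
- Apply the same rule to any value missing at the interim look, with the 2.9626 boundary unchanged. Keep the model short: with about 26 observed patients per arm, the nine-coefficient model is unstable (early crossing 12.6%, against 20.0% for baseline only).
- Move zero change to a sensitivity analysis beside complete-case.
- Add a delta-adjusted tipping-point analysis that keeps observed baselines. This also resolves the ambiguous worst-case wording.

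The cost is document wording and modest programming; N stays at 128. At 20% missing, power falls about 1 point with a baseline-only model (90.6% to 89.6%; 90.2% to 89.2% with the interim look, under the assumption of 20% missing there). It falls about 3 points, to 87.7%, if site and all covariates are included and predict nothing. At 10% missing the baseline-only loss is about 0.3 points (93.6% to 93.3%). The reported interval will be wider (SE 0.386 against 0.307 at 20% missing), and the result relies on missing at random, which the tipping-point analysis tests.

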4(c)(iv). Baseline Data Collection: A complete history and physical, 12-lead electrocardiogram, lipid panel, basic metabolic panel (BMP) with LFT, complete blood count, and complete cardiac catheterization, PCI, IVUS-VH and adjunctive pharmacotherapy data will be collected on all eligible patients apart from demographic and contact information.

4(c)(v). Stratification and Randomization: Prior to randomizing a patient, all screening and baseline assessments must be completed and the patient determined to be eligible for inclusion in the study. Eligible patients will be randomized to one of two treatment groups (ILLT or SMT) following an uncomplicated index PCI. 40-80mg daily Atorvastatin or equivalent statin medication treatment (ILLT or SMT) will be initiated within 24h after randomization and LDL-apheresis for ILLT group will be initiated within 36 hours of hospital admission unless the 36-hour window is mandatory for those who were on ACE inhibitors to allow for the complete washout of ACE inhibitors. Refer to **Figure 8** for all study timelines. Screening and randomization will be performed by a study coordinator, and LDL-apheresis will be conducted by a contracted specialized apheresis nurse.

4(c)(v)(1). Randomization Methods: The randomization scheme and associated codes will be developed by the Cooperative Studies Program Coordinating Center (CSPCC). Permuted block randomization with random block sizes will be employed to assign patients to either ILLT or SMT in a 1:1 ratio. The randomization will be stratified by investigation sites only.

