## **Baseline Characteristic Comparisons**

Patient characteristics and outcome measures at baseline will be compared between the two treatment groups (ILLT vs. SMT) to determine if the treatment arms differ on any important variables. The chi-square test or Fisher's exact test will be used for categorical variables and the t-test for two independent samples will be used for continuous variables as shown in the following sample table:

Variable	ILLT		SMT		p-value
	N	Mean±SD (or %)	N	Mean±SD (or %)	
Age (yrs)					
Male(%)					

The following data will be summarized using the table format above:

- Demographics
- Clinical Evaluations
- Lab Tests
- Medical History
- Index PCI Results
- Index PCI Complications
- IVUS-VH Chart
- EPC Counts
- Medications Usage – Dosage

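### Neither the t-test on change nor the supporting ANCOVA adjusts for baseline atheroma volume or site; prespecifying both is a modest gain that needs only wording

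*Protocol*

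**What the plan says.** **Primary analysis.** The SAP (Analysis of Primary Effectiveness Outcome) states that the change in total atheroma volume "from baseline to 90-day follow-up will be analyzed using the two-sample t-test". Protocol 4(g)(iv) says the same. Both set the change to 0 when the 90-day measurement is missing.

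**Supporting analysis.** Both documents add an ANCOVA of the "treatment effect on primary effectiveness outcome adjusting for age, pre-existing CAD, pre-existing diabetes, and baseline LDL levels". That list is closed: four covariates, none of them baseline volume or site.

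**%NC.** The SAP (Analysis of Secondary Effectiveness Outcomes) repeats the pattern: "The change of %NC component of atheroma from baseline to 90-day follow-up will be analyzed using the two-sample t-test", followed by an ANCOVA with the same four covariates. Protocol 4(g)(v)(1) matches.

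**Site.** Protocol 4(c)(v)(1): "The randomization will be stratified by investigation sites only". Protocol 4(g)(viii) adds that "separate analyses will be performed across 4 participating sites for each treatment group in order to evaluate the site effect" and to justify pooling.

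**Availability of the covariates.** Protocol 4(c)(iv): "complete cardiac catheterization, PCI, IVUS-VH and adjunctive pharmacotherapy data will be collected on all eligible patients". Protocol 4(c)(v): "Prior to randomizing a patient, all screening and baseline assessments must be completed". The SAP (Baseline Characteristic Comparisons) also plans that "Patient characteristics and outcome measures at baseline will be compared between the two treatment groups".

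**The concern.** A change score subtracts baseline with a slope of exactly 1. If the true regression slope of 90-day volume on baseline is below 1, as regression to the mean implies, change still depends on baseline. An arm that starts lower by chance will then tend to show less regression. The t-test estimate moves with that imbalance, for or against ILLT, and the supporting ANCOVA does not correct it because baseline volume is not among its covariates.

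The SAP compares the arms on the baseline outcome measures but plans no treatment comparison that uses them. If an imbalance appears, any adjustment for it would be post hoc and open to challenge.

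For site, the by-site analyses check pooling within each arm; they do not give a site-adjusted treatment effect. An analysis that ignores the stratification factor does not credit the precision that stratification bought.

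At stake are a little average power and, more usefully, protection of the estimate against a chance imbalance.

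**Working it through.** **1. The plan's own figure.** The SDs 2.08 and 1.75 give a pooled SD of √((2.08² + 1.75²)/2) = 1.922. For d = 0.65, two-sided α = 0.05 and 90% power, the exact t calculation gives 51 per arm, and 102/0.8 = 127.5, so 128. The stated sample size reproduces.

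**2. Expected effect under the missing-data rule.** With 20% of changes set to 0, the difference is 0.8 × 1.26 = 1.008. The variances become 0.8 × 2.08² + 0.16 × 0.38² = 3.484 and 0.8 × 1.75² + 0.16 × 0.88² = 2.574, so the pooled SD is 1.740. Power with 64 per arm is about 90%.

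**3. Assumptions not in the documents.** The correlation r between baseline and 90-day volume is taken as 0.95, 0.90 or 0.70, with zeros occurring at random. The nearest figures are same-session reproducibility coefficients in Protocol 3(d): 0.95 for plaque burden and 0.90 for necrotic core. They are imperfect guides to a 90-day correlation. Nothing in the documents supports 0.70, which serves as a pessimistic end. Let k be the ratio of the 90-day SD to the baseline SD. Then:

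- baseline SD = 1.922/√(1 + k² − 2rk)
- slope of change on baseline = rk − 1
- shift from a 2-SE baseline imbalance = 0.8 × 2 × √(2/64) × |rk − 1| × baseline SD

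For k = 1 and r = 0.90: baseline SD = 1.922/√0.2 = 4.298, and the shift is 0.8 × 0.3536 × 0.10 × 4.298 = 0.122, which is 12% of 1.008.

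**4. Results for k = 1** (60,000 simulated trials per cell, one two-sided test at 0.05; Monte Carlo SE √(0.9 × 0.1/60,000) = 0.12 points):

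| | r = 0.95 | r = 0.90 | r = 0.70 |
|---|---|---|---|
| Type I error, t-test | 5.0% | 5.1% | 4.9% |
| Average power, t-test | 90.7% | 90.4% | 90.4% |
| Average power, ANCOVA with baseline | 91.1% | 91.2% | 93.5% |
| Shift from 2-SE imbalance | 0.086 (9%) | 0.122 (12%) | 0.211 (21%) |
| t-test power, ILLT 2 SE lower (unfavourable) | 85.4% | 82.6% | 75.1% |
| t-test power, ILLT 2 SE higher (favourable) | 94.6% | 96.0% | 98.4% |
| ANCOVA power, unfavourable | 90.4% | 90.9% | 93.0% |
| ANCOVA power, favourable | 90.3% | 90.8% | 93.0% |

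Hand check of the unfavourable row: the SE is 1.740 × √(2/64) = 0.308, and Φ((1.008 − shift)/0.308 − 1.96) gives about 85%, 82% and 74%.

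An imbalance of at least 2 SE occurs about 1 time in 20, and about 1 in 40 in the unfavourable direction. Both directions are already averaged in the roughly 90%.

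**5. Sensitivity to equal SDs:**

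| | r = 0.95 | r = 0.90 | r = 0.70 |
|---|---|---|---|
| k = 0.95: shift | 17% | 18% | 24% |
| k = 0.95: gain in average power (points) | +1.8 | +2.2 | +3.9 |
| k = 1.05: shift | 0.4% | 6% | 18% |
| k = 1.05: gain in average power (points) | −0.3 | +0.1 | +2.0 |

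**6. %NC.** No planning SD is given. In units of the SE of the difference, a 2-SE imbalance shifts the estimate by √0.8 × 2 × √((1 − r)/2) = 0.28, 0.40 and 0.69 for the same three values of r.

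**7. Site.** Four equal sites balanced by arm, with assumed shares of the variance of change (100,000 trials per cell):

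| Share due to site | 0% | 2% | 5% | 10% |
|---|---|---|---|---|
| Type I error, t-test | 4.98% | 4.82% | 4.38% | 4.03% |
| Power, t-test | 90.46% | 90.65% | 90.99% | 91.54% |
| Power, site-adjusted | 90.42% | 90.89% | 91.64% | 92.80% |

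**The case against.** The plan contains no error here. A prespecified t-test on change with a supporting covariate model is legitimate, it is unbiased under randomisation, and ignoring site is conservative. At r of 0.95 and 0.90 the average gain is under one point, and at r = 0.95 even its sign depends on an SD ratio that nobody knows. The large conditional losses need an uncommon imbalance and, at their worst, an r with no support in the documents. The baseline table would make any imbalance visible. Replacing the primary test also touches the interim statistic in a programme that FDA and the DMC already follow.

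Most of this stands as a limit on size, and it is why the gain is called modest. Two further limits also stand:

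- The inputs 1.26 and 1.922 are plaque areas in mm² at one year in familial hypercholesterolaemia, whereas the endpoint is a volume at 90 days. Only the relative shifts carry over, and only if d = 0.65 does.
- Baseline images are acquired before randomisation, but Protocol 4(e) does not say when the blinded core laboratory reads them. The covariate is valid all the same.

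None of this justifies leaving both terms out. A table that shows an imbalance does not adjust for it. The largest average power loss in the cases examined is 0.3 points. The smaller repair leaves the primary test and the interim rule alone.

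**Conclusion.** The concern holds. In both documents the primary and %NC comparisons, and their supporting ANCOVAs, omit the baseline value of the outcome and the only stratification factor. Validity and sample size are not in question: type I error stays at or below about 5%, and 128 stands.

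With equal SDs the average power gain from baseline volume is 0.4, 0.8 or 3.1 points for r of 0.95, 0.90 or 0.70. The main benefit is an estimate that a 2-SE baseline imbalance no longer moves by 9%, 12% or 21% of the expected effect. Site contributes at most 1.3 points over the assumed range. Neither r, the SD ratio nor the between-site variance is given in the documents, so these are ranges and not predictions. The change is worth making because it costs so little. It does not address the separate effect of setting missing changes to 0, which shrinks the expected difference whichever model is used.

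**What to change.** **Preferred.** In Protocol 4(g)(iv) and SAP, Analysis of Primary Effectiveness Outcome, make the primary analysis an ANCOVA of change in total atheroma volume on treatment, baseline atheroma volume and site, with the two-sample t-test as supportive. Do the same for %NC with baseline %NC and site, in Protocol 4(g)(v)(1) and SAP, Analysis of Secondary Effectiveness Outcomes. In those two places the ANCOVA sentence names the primary outcome and should name %NC. The four listed covariates may stay, but the text must say whether they enter the primary model; the simplest course is to keep them for a supportive model that also contains baseline and site. Use the standardised ANCOVA treatment statistic at the interim look, and align Protocol 4(g)(vii), SAP Plan for Interim Analysis, and the two-sample t-test named in SAP Plan for Presenting Data to DMC.

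**Smaller repair.** Keep the t-test as primary and add the baseline outcome value and site to the existing ANCOVAs. Only the primary and %NC analysis paragraphs change; the interim text does not.

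**Cost.** Wording only: no new patients, visits or measurements. Protocol section 4 reports that first-stage efficacy data have gone to FDA, and the SAP counts the end of that stage as an interim look. The amendment should therefore be made and dated before anyone sees unblinded effectiveness data from the pivotal stage.
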